### **Study Populations**

The primary analysis population will be the full analysis set (FAS) excluding subjects taking rescue pain medications or second dose of study medication within the first 2 hours postdose.

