**Exploratory Objectives**

Study Design:	
This is a randomized, double-blind study, with an open-label extension, to be conducted at approximately 18 centers in the United States (US). Male and female subjects, 18-65 years old (inclusive), previously diagnosed with episodic migraine (at least 12 months medical history prior to screening) who do not have medication overuse headaches (MOH), who experience 2 to 6 migraine attacks (with or without visual aura) per month, with 14 or fewer migraine headache days per month, and who can demonstrate 48 hours of headache free time between migraine attacks, will be initially randomized in a 1:1 ratio in a double-blind fashion to receive by subcutaneous (SC) injection either DFN-11 or placebo, to be used in 1 migraine attack within 1 hour of experiencing moderate to severe pain level. This double-blind period is up to 4 weeks (+ 3 days) or within 5 days (+ 3 days) postdose, whichever is earlier, depending on when, and if, the subject will get migraine attack during the double-blind period. Subjects may subsequently continue into an open-label period where they will receive active DFN-11 for 8 weeks to treat their migraine within 1 hour of migraine pain onset at any pain level.
 
During the 2 treatment periods, data regarding the study medication effect and the associated impact on function and subjects' satisfaction will also be collected. All subjects will receive the study medication via self-administered SC injections (DFN-11 or placebo) using an autoinjector during the study. After study completion or discontinuation, subjects should be referred to their usual healthcare professional to resume pre-study standard of care, as per the Investigator's discretion. Subjects will return the autoinjector to the study site at the end of the study.
 
During both treatment periods of the study, subjects will have an option to take another dose of study medication, if they experience relief but feel the first dose is insufficient, or rescue medication 2 hours after the first dose of study medication if required and after the efficacy data has been recorded. No more than 2 doses of study medication will be taken in a 24 hour period. Rescue medication will be decided between the Investigator and the subject.

Selection of Subjects:	
Main Inclusion Criteria:
 
Subjects may be included in the study if they meet the following criteria:

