	

1. Able and willing to provide written informed consent

2. Male or female, 18 to 65 years of age, inclusive, at screening

 
Notes:
 

a. If female, a subject must have a negative serum pregnancy test at screening, does not plan to become pregnant during the study, and is not lactating

b. If female, a subject also must have a negative urine pregnancy test at all subsequent study visits after the Screening Visit, and agree to practice a reliable form of contraception or abstinence during the study (except if surgically, or otherwise, sterile or >1 year post-menopausal). Acceptable forms of contraception include implants, injectables, combined oral contraceptives, an intrauterine device, a vasectomized partner, an exclusively female partner, and double-barrier methods.

c. If male (with female partner), a subject must agree to practice a reliable form of contraception or abstinence during the study.

 

3. A history of episodic migraine (using International Classification of Headache Disorders criteria, 2nd edition [ICHD II]) who experience 2 to 6 migraine attacks a month for at least the past 12 months with no more than 14 migraine headache days per month, and with 48 hours of headache free time between migraine headaches

4. Have migraine with or without aura; if with aura, the aura cannot last longer than 60 minutes

5. Subjects who, in the opinion of the Investigator, are willing and able to:

• Evaluate and record pain, migraine symptoms, and study medication effectiveness information in real time using a subject eDiary for the duration of the study

• Record each instance of the use of study medication and rescue medication in real time using a subject eDiary for the duration of the study

• Comply with all other study procedures and scheduling requirements

--	--

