	
3 months prior to screening and is expected to remain stable throughout the study
 
Note: For the above-mentioned conditions, the site must have appropriate documentation to justify the mentioned drug use (e.g., documented medical history and a valid prescription-based dispensation)
 

33. A history of or current neurological or psychiatric impairment, including but not limited to psychosis, current major depression, bipolar disorder or cognitive dysfunction that, in the opinion of the Investigator, would compromise data collection

34. Subjects who have received treatment with an investigational drug or device within 30 days of the screening visit or participated in a central nervous system clinical trial in the 3 months prior to screening

35. Subjects with any other medical condition that, in the judgment of the Investigator and/or Medical Monitor, would confound the objectives of the study (e.g., positive screening test for human immunodeficiency virus [HIV], hepatitis B surface antigen positive or hepatitis C positive, a known history of systemic lupus erythematosus)

36. History of cancer within the past 5 years (except adequately treated basal cell or squamous cell skin carcinoma or in situ cervical cancer)

37. History of any skin condition that may adversely affect the injection or use of subcutaneously administered medication such as scleroderma

38. Subjects who should not be enrolled per the precautions, warnings, and contraindications section of the Imitrex® product label or package insert

39. Subjects who plan to donate blood, sperm, or oocytes during the study and for 30 days after the last dose of study medication

40. Subjects who are employees or immediate relatives of the employees of the Sponsor, any of its affiliates or partners, or of the study center

Planned Sample Size:	A total of approximately 266 subjects will be randomized in a 1:1 ratio into 2 treatment arms. The study may be stopped sooner based on an independent Data Monitoring Committee (DMC) recommendation after reviewing study efficacy data

	(see Statistical Methods and Planned Analysis section for details) at an interim analysis (IA).
Investigational Therapy:	DFN-11 Injection (sumatriptan 3 mg)
Reference Therapy:	Placebo injection

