Study Endpoints:	
Primary Endpoints:
 
Double-Blind Period (Period 1)
 
The proportion of subjects who are pain-free (defined as a reduction from predose moderate [Grade 2] or severe [Grade 3] pain to none [Grade 0]) 2 hours after the first dose of study medication compared between DFN-11 and placebo in the double-blind period.
 
Key Secondary Endpoints:
 
Double-Blind Period (Period 1)
 

• [REDACTED]

• The proportion of subjects who are pain-free (defined as a reduction from predose moderate [Grade 2] or severe [Grade 3] pain to none [Grade 0]) 1 hour after the first dose of study medication compared between DFN-11 and placebo in double-blind period.

• The proportion of subjects who are free from their MBS among nausea, photophobia, and phonophobia 2 hours after the first dose of study medication compared between DFN-11 and placebo in double-blind period.

 
Other Secondary Endpoints:
 
Double-Blind and Open-Label Extension (Period 1 and Period 2)
 
Efficacy Endpoints
 
The secondary efficacy endpoints are as follows:
 

• [REDACTED]

	

• The proportion of subjects who have pain relief [REDACTED]

• The proportion of subjects who are pain-free [REDACTED]

• The proportion of subjects with their MBS absent [REDACTED]

• Change in functional disability score [REDACTED]

• The proportion of subjects who use a second dose of the study medication or rescue medication after 2 hours (2-24 hours) postdose study medication compared between DFN-11 and placebo in double-blind period, and DFN-11

--	---

in the open-label period

- Treatment satisfaction at 2 hours postdose as determined on a 7 point scale after study medication compared between DFN-11 and placebo in double-blind period, and DFN-11 in the open-label period.
- Treatment satisfaction as measured by PPMQ-R at 24 hours postdose study medication compared between DFN-11 and placebo in double-blind period, and DFN-11 in the open-label period.

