### **Primary Efficacy Analysis**

The primary efficacy analysis will be performed using Fisher's exact test.

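### The primary analysis removes subjects who take rescue or a second dose within 2 hours instead of counting them as not pain-free

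*Combined protocol and SAP*

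**What the plan says.** All references are to Section 1 (Synopsis) of the combined protocol and SAP.

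- **Study Populations:** the primary population is the "full analysis set (FAS) excluding subjects taking rescue pain medications or second dose of study medication within the first 2 hours postdose". The FAS itself is not defined in the text available.
- **Study Endpoints, Primary Endpoints:** the endpoint is "The proportion of subjects who are pain-free (defined as a reduction from predose moderate [Grade 2] or severe [Grade 3] pain to none", that is Grade 0, assessed "2 hours after the first dose of study medication compared between DFN-11 and placebo in the double-blind period". It has no rule for subjects who took other medication before the assessment.
- **Primary Efficacy Analysis:** "The primary efficacy analysis will be performed using Fisher's exact test". Nothing is added about how early users are scored, and no sensitivity analysis keeps them.
- **Study Design:** subjects may take a second dose, or "rescue medication 2 hours after the first dose of study medication if required and after the efficacy data has been recorded". Use before 2 hours is therefore a departure from the design.
- **Other Secondary Endpoints:** one endpoint counts subjects who use a "second dose of the study medication or rescue medication after 2 hours (2-24 hours) postdose".

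The Statistical Methods introduction leaves the detail of secondary and exploratory endpoints to the SAP but says that the primary method is given there. The exclusion would therefore apply as written.

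**The concern.** Whether a subject belongs to the primary set is settled after randomisation and after dosing, by an event that treatment can change. Blinding does not prevent this, because efficacy and side effects can drive early use even when nobody knows the allocation.

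Subjects who reach for more medication before 2 hours have mostly not become pain-free. Excluding them raises the apparent pain-free rate in each arm, and raises it more in the arm with more early use. The early use is also outside the rescue endpoint, whose window opens at 2 hours; such a subject counts there only if medication is taken again later.

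The direction is not fixed in advance. If the drug works, more early rescue on placebo is the more plausible pattern. That flatters placebo and costs power. The reverse imbalance exaggerates the benefit and raises the chance of a false claim for DFN-11. The reverse is not far-fetched for second doses, because the Study Design text offers them to subjects who had some relief but not enough, and an active drug may produce more such subjects.

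**Working it through.** **Inputs from the documents.** "A total of approximately 266 subjects will be randomized in a 1:1 ratio into 2 treatment arms", so about 133 per arm; Fisher's exact test; the endpoint and exclusion above.

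**The plan's own figure.** The 266 cannot be reproduced, because the text gives no response rates, power, numeric alpha or dropout. A scan of assumed inputs found 172 combinations within 3% of 266 (for example 30% against 50%, 80% power and 30% loss gives exactly 266). The figure is neither confirmed nor contradicted, and it cannot tell us which rates the sponsor had in mind.

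**Assumptions, not from the documents.** Two-sided 0.05; all 133 per arm dosed; no alpha spent at interim; early users not pain-free; the response and early-use rates shown.

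**Formula.** Let p be the true pain-free rate in an arm when early users count as failures, and q its early-use rate. All the pain-free subjects stay in and a fraction q of the arm is removed, so the analysed rate is p/(1−q). Retained size is 133 × (1−q), rounded. Example for q = 2% on DFN-11 and 10% on placebo: 0.40/0.98 = 40.8%, 0.25/0.90 = 27.8%, difference 13.0 points; sizes 130 and 120.

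**True effect, 40% against 25%** (exact enumeration of Fisher's test):

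| Early use, DFN-11 / placebo | Retained | Analysed rates | Difference | Power |
|---|---|---|---|---|
| none excluded (full FAS) | 133 / 133 | 40.0% / 25.0% | 15.0 points | 70.4% |
| 1% / 3% | 132 / 129 | 40.4% / 25.8% | 14.6 points | 69.5% |
| 2% / 10% | 130 / 120 | 40.8% / 27.8% | 13.0 points | 55.8% |
| 3% / 1% | 129 / 132 | 41.2% / 25.3% | 16.0 points | 76.4% |
| 10% / 3% | 120 / 129 | 44.4% / 25.8% | 18.7 points | 86.3% |

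**No true effect, 30% in both arms:**

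| Early use, DFN-11 / placebo | Spurious difference | False claim for DFN-11 | False claim for placebo |
|---|---|---|---|
| none excluded (full FAS) | 0 | 1.85% | 1.85% |
| 1% / 3% | −0.6 points | 1.81% | 2.53% |
| 3% / 1% | +0.6 points | 2.53% | 1.81% |
| 10% / 2% | +2.7 points | 6.09% | 0.62% |
| 5% / 15% | −3.7 points | 0.41% | 7.75% |

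Letting the number of early users vary binomially instead of fixing it moved the figures by at most 0.7 points.

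**Second check with other rates.** A simulation (8,000 runs per scenario) at 50% against 30% gave a difference of 20.0 points and about 90% power when early users count as failures, whatever the early-use rates. Under exclusion it gave 19.9 points and 90% at 1%/2%, 19.4 points and 87% at 2%/5%, 15.1 points and 62% at 5%/20%, and 24.0 points and 96% at 10%/5%. With no true effect at 30%, early use of 20%/5% gave 14.0% false claims for DFN-11, against about 2% when early users count as failures.

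**The case against.** The strongest reply is that early use will be rare and that the likely bias is conservative. The design does not allow medication before 2 hours, so each case is a deviation. At 1–3% early use the tables show little movement, particularly in the more plausible direction: at 1%/3%, power drops by about one point and false claims for DFN-11 do not rise. The larger distortions need a deviation rate near 10% in one arm and a marked imbalance, and nothing in the documents points to either. This stands, and it limits the weight of the point. It does not remove it: the documents give no expected frequency, and the sponsor thought early use likely enough to write an exclusion for it.

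Three further points also stand as limits:

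- The FAS is undefined here and may already leave out randomised subjects who never treated an attack. The finding concerns only the early-use exclusion; the full FAS is closer to the randomised groups but may not equal them.
- The expression p/(1−q) holds only if early users are regarded as not pain-free. Under a target that takes observed 2-hour pain whatever was used, some of them might be pain-free.
- Early use is not lost from the record, since the Safety text lists study and concomitant medication use. A listing does not, however, put those subjects back into the primary comparison.

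One could also say that a 2-hour score taken after rescue is contaminated. That is a reason not to use the score at face value, but it does not justify discarding the subject.

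**Conclusion.** The concern holds. As written, the primary analysis discards subjects on a post-dose event that treatment can affect, and no rule in the text counts them as failures. Confidence is high on the principle and low on the size, because early-use rates are not given.

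On the assumptions stated, the effect is minor when early use is 1–3%. It becomes material with a large imbalance: about 15 points of power lost at 2%/10% (70.4 − 55.8 = 14.6), or a false-claim rate for DFN-11 about 3.3 times its full-FAS value at 10%/2% (6.09/1.85 = 3.3). The direction cannot be known beforehand. This should be fixed because the remedy costs almost nothing, although serious harm is not shown to be likely.

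**What to change.** 1. Make the full FAS, analysed by randomised arm, the primary population, and define the FAS in the same place.
2. State that a subject who took rescue or a second dose before the 2-hour assessment is counted as not pain-free at 2 hours, whatever pain score was recorded (a composite strategy).
3. Tabulate use before 2 hours by arm.
4. Keep the present exclusion as a sensitivity analysis.
5. Settle this before anyone sees unblinded interim data, since interim looks for efficacy are planned.

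For consistency, the SAP could apply a matching rule to the 1-hour pain-free and 2-hour most-bothersome-symptom endpoints, with the cut-off at each endpoint's own assessment time. The Study Populations text does not set their population, so this is only a suggestion.

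The cost is a sentence or two in the protocol and SAP and one extra table. No new data or subjects are needed, because subjects must already be able to "Record each instance of the use of study medication and rescue medication in real time using a subject eDiary". Reported pain-free rates will be slightly lower in any arm with early use.

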### **Primary Efficacy Analysis**

The primary efficacy analysis will be performed using Fisher's exact test.

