Treatment Duration:	The duration of study participation will be approximately 15 weeks, including screening period of approximately 3 weeks, double-blind treatment period of up to 4 weeks (+ 3 days) or within 5 days (+ 3 days) postdose, whichever is earlier, and an open-label treatment period of 8 weeks ( $\pm$ 3 days).
Criteria for Evaluation:	
Efficacy:
 

Subjects will be provided with an eDiary at Screening Visit (Visit 1) to collect at least 1 migraine episode data in real time and, if randomized, to continue to collect migraine data in real time through End of Treatment (ET) Visit (Visit 5/ET):

Migraine pain start and end (date and time)

Level of headache pain predose and at various timepoints postdose (Levels: 0 = none; 1 = mild; 2 = moderate; 3 = severe)

[REDACTED]

Migraine symptoms and MBS other than pain: nausea, photophobia, and phonophobia, predose and at various timepoints postdose

PPMQ-R

Functional disability scale (0 = no disability, able to function normally; 1 = performance of daily activities mildly impaired, can still do everything but with difficulty; 2 = performance of daily activities moderately impaired, unable to do some things; 3 = performance of daily activities severely impaired, cannot do all or most things, bed rest may be necessary)

Treatment satisfaction (7 point scale)

Study medication and rescue use

 
Safety:
 

Adverse events: Adverse events will be collected from signing of the informed consent form (ICF) at Screening Visit (Visit 1) until a subject's completion or discontinuation from the study

Concomitant medication review

	

Physical examinations

Pregnancy tests in females

Measurement of vital signs (sitting systolic and diastolic blood pressure, pulse rate, and body temperature)

Clinical laboratory examination (hematology, chemistry, and urinalysis)

Urine drug screen

12-lead ECG

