## Exploratory Endpoints:

A high-contrast, black and white image showing a series of horizontal bars of varying lengths. The bars are mostly black on a white background, with some white bars appearing on the right side. A small orange dot is located at the bottom left.

	

• [REDACTED]

[REDACTED]

[REDACTED]

[REDACTED]

[REDACTED]

Statistical Methods and Planned Analyses:	The statistical analysis method for the primary endpoint is described below. Detailed analyses of secondary and exploratory endpoints will be provided in the Statistical Analysis Plan (SAP), which will be finalized before database lock and unblinding of the data.

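### The primary Fisher's exact test is valid but conservative and ignores the recorded predose pain grade; a stratified Cochran-Mantel-Haenszel (CMH) test would gain a few points of power at little cost

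*Combined protocol and SAP*

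**What the plan says.** In the Synopsis (Section 1), the row on statistical methods and planned analyses states: "The statistical analysis method for the primary endpoint is described below". It leaves only the secondary and exploratory analyses to the SAP. Under Primary Efficacy Analysis the entire description is: "The primary efficacy analysis will be performed using Fisher's exact test". No stratification factor, covariate, alpha or sidedness is named.

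Under Planned Sample Size: "A total of approximately 266 subjects will be randomized in a 1:1 ratio into 2 treatment arms". That is 266 / 2 = 133 per arm randomized. Under Study Populations, the primary population is the full analysis set "excluding subjects taking rescue pain medications or second dose of study medication within the first 2 hours postdose", so the number analysed may be below 133. Under Interim analysis, one or more efficacy looks are planned with a conservative spending function, but no boundaries are given.

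Under Study Design, subjects are "initially randomized in a 1:1 ratio in a double-blind fashion to receive by subcutaneous (SC) injection either DFN-11 or placebo". Each subject treats a single attack in this period, soon after pain has become at least moderate. The efficacy criteria have the eDiary record headache pain before dosing on a 0-3 scale, and the primary endpoint counts a subject as pain-free only from predose Grade 2 or 3.

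**The concern.** Fisher's test conditions on the total number of responders. The conditional distribution is discrete, so the attained type I error usually falls well short of the nominal level. The unused part of alpha is power given away.

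The plan also holds a plausible baseline variable that the test ignores. Predose grade is recorded after randomization but before a blinded dose, so treatment cannot affect it. It is a legitimate stratifier among subjects who treat an attack. If severe attacks clear less often than moderate ones, comparing arms within grade is more efficient than pooling.

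What is at stake is a modest amount of power, available from the same subjects and data. The validity of the trial's conclusion is not in question.

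**Working it through.** **The plan's own figure.** The total of 266 cannot be reproduced, because the supplied text gives no alpha, sidedness, power, response rates or dropout.

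**Inputs.** From the documents: 133 per arm, a binary endpoint, an unadjusted Fisher's exact test, and predose grade recorded. Assumed: two-sided 0.05 at a single look, 45% of attacks severe, and the response rates below.

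**Step 1: size of Fisher's test.** All tables (x, y) with n per arm were enumerated:

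size(p) = sum over x, y of Bin(x; n, p) × Bin(y; n, p) × 1{Fisher p-value ≤ 0.05}.

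| Common null rate | 10% | 20% | 30% | 40% | 50% |
|---|---|---|---|---|---|
| Fisher size, n = 133 | 3.06% | 3.60% | 3.70% | 3.88% | 4.28% |
| Boschloo size, n = 133 | 4.07% | 4.45% | 4.66% | 4.93% | 4.30% |

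The maximum for Fisher over all null rates is 4.28%, so the test is valid. With 113-126 per arm its size is about 2.8-3.9% for null rates of 10-50%. If interim spending left a final nominal level of 0.048 (assumed), the size at 133 per arm would be 3.05%, 3.56% and 3.24% at null rates of 10%, 30% and 50%.

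**Step 2: alternatives.** Boschloo's test uses the Fisher p-value as its statistic and raises the cut-off until the maximum size over all null rates just stays below 0.05. At 133 per arm the cut-off is 0.0623 and the maximum size is 4.95%.

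The CMH statistic over grades h, without continuity correction, is

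[Σ(a_h − n_1h m_h / N_h)]² / Σ[n_1h n_0h m_h (N_h − m_h) / (N_h² (N_h − 1))], compared with 1.96² = 3.84.

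Here a_h is the number of pain-free subjects on DFN-11, m_h the pain-free total, n_1h and n_0h the arm sizes, and N_h their sum. Its simulated size at 133 per arm is 4.9-5.1%.

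**Step 3: power at 133 per arm.** Placebo rates (moderate / severe) are: (a) 25 / 25, not prognostic; (b) 30 / 22, weakly prognostic; (c) 35 / 15, strongly prognostic. Active rates follow from a common odds ratio (OR). For example, at OR 2.0 a rate of 25% becomes 0.25 × 2 / (0.75 + 0.25 × 2) = 40%. There were 1,000,000 simulated trials per row.

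| Case | OR | Fisher | Boschloo | CMH | CMH − Fisher | Stratifier alone |
|---|---|---|---|---|---|---|
| a | 2.0 | 70.4 | 73.6 | 74.5 | 4.1 | 0.0 |
| b | 2.0 | 70.4 | 73.9 | 75.1 | 4.7 | 0.5 |
| c | 2.0 | 65.1 | 68.8 | 72.4 | 7.3 | 2.8 |
| a | 2.45 | 91.2 | 92.8 | 93.1 | 1.9 | 0.0 |
| b | 2.45 | 91.2 | 92.9 | 93.3 | 2.1 | 0.2 |
| c | 2.45 | 87.4 | 89.6 | 91.6 | 4.2 | 1.8 |

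The last column compares CMH with the same statistic unstratified. In case (c) at OR 2.0, leaving Fisher's test accounts for 7.3 − 2.8 = 4.5 points and the stratifier for 2.8.

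**Step 4: fewer analysed.** Exact power for 25% vs 40%:

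| Per arm | Fisher | Boschloo | Gain |
|---|---|---|---|
| 133 | 70.4 | 73.6 | 3.2 |
| 126 | 68.1 | 70.0 | 1.9 |
| 120 | 65.4 | 69.7 | 4.3 |
| 113 | 62.8 | 65.9 | 3.1 |

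The gain does not move smoothly with n, because both tests step over a discrete set of tables. Across the six scenarios at 113-126 per arm, Boschloo adds 0.8-4.6 points. CMH adds 1.8-5.3 in (a) and (b), and 4.3-7.7 in (c).

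**Step 5: the stratum rule.** Suppose 5% of subjects have a missing or Grade 0-1 predose grade, are counted as not pain-free and are pooled with Grade 2. At OR 2.0 the Fisher / Boschloo / CMH power is 67.1 / 70.5 / 71.4 in (a) and 61.7 / 65.3 / 68.2 in (c). CMH size stays at 4.97-5.00% with 2%, 5% or 10% of subjects affected.

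**The case against.** Fisher's exact test is a recognised primary test for a 1:1 binary comparison. It needs no large-sample argument and no rule for odd predose grades. Giving up an exact guarantee for a few points of power is the sponsor's judgement. If 266 was computed for Fisher's test, there is no shortfall to repair. All of this stands, and it is why the point is an option to consider.

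Three stronger readings are tempting, and the documents do not support them.

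- A reader might infer that ignoring predose grade is the main loss. It is not: unless grade is strongly prognostic, the stratifier alone adds at most about half a point. Nothing in the documents says how prognostic grade is.
- A reader might take the 3.2-point Boschloo gain at 133 per arm as general, or its equivalent of 18 extra subjects (Fisher's test needs 142 per arm to match it at 25% vs 40%; 2 × 9 = 18). Both are specific to 133 per arm. At 126 the gain is 1.9, and the primary population may well be smaller than the number randomized.
- A reader might infer that no adjusted analysis exists anywhere. The supplied statistical text is a synopsis, and supportive adjusted analyses may stand in text not supplied. The point concerns the named primary test only.

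The CMH test does give up Fisher's strict size control. Part of its gain is simply the use of the full 5%.

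**Conclusion.** This is a cheap improvement, not an error. The named test is valid and conservative: true size 3.1-4.3% under the single-look assumptions of Step 1. The first figure is for a 10% null rate; at lower rates the size is smaller still. With alpha spent at an interim, the final-look size would be no higher than this.

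A CMH test stratified by predose grade would add about 2-5 points of power, or about 4-7 if grade is strongly prognostic, with the smaller gains near 90% power. These figures rest on assumed rates and severe share. The documents do not support a claim that the trial is underpowered or its type I error uncontrolled. Confidence is high in the size calculation and moderate in the practical benefit.

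**What to change.** Before any unblinded look, replace the sentence under Primary Efficacy Analysis along these lines:

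*The primary analysis will be a two-sided Cochran-Mantel-Haenszel test, without continuity correction, of the proportion pain-free at 2 hours, DFN-11 against placebo, stratified by predose pain grade (2 or 3). The Mantel-Haenszel risk difference with its 95% confidence interval will be reported. The same statistic will be used at each interim and at the final analysis, with boundaries stated for it. Fisher's exact test will be a sensitivity analysis.*

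State in advance how subjects in the primary population with a missing or Grade 0-1 predose grade are handled. One workable rule is to count them as not pain-free, since the endpoint requires predose Grade 2 or 3, and to place them in the Grade 2 stratum.

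If a strict size guarantee is preferred, make Boschloo's exact test primary, with its critical value derived at each look's nominal alpha and for the number analysed. It needs no stratum rule but does not use predose grade.

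The cost is wording in the protocol and SAP, interim boundaries stated for the chosen statistic, and a recheck of the sample size with alpha, power and response rates written down. No new data are needed. The downside of CMH is asymptotic rather than exact size control, with simulated size about 5.0%.
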